## List of abbreviations and relevant definitions

AE	Adverse Event
CA	Competent Authority
CCMO	Central Committee on Research Involving Human Subjects; in Dutch: Centrale Commissie Mensgebonden Onderzoek
DSMB	Data Safety Monitoring Board
EudraCT	European drug regulatory affairs Clinical Trials
IC	Informed Consent
METC	Medical research ethics committee (MREC); in Dutch: medisch ethische toetsing commissie (METC)
(S)AE	(Serious) Adverse Event
Sponsor	The sponsor is the party that commissions the organisation or performance of the research, for example a pharmaceutical company, academic hospital, scientific organisation or investigator. A party that provides funding for a study but does not commission it is not regarded as the sponsor, but referred to as a subsidising party.
SUSAR	Suspected Unexpected Serious Adverse Reaction
TEM	Transanal Endoscopic Microsurgical Excision
TAMIS	Transanal Minimal Invasive Surgery
eFTR	Endoscopic Full-Thickness Resection
Wbp	Personal Data Protection Act (in Dutch: Wet Bescherming Persoonsgegevens)
WMO	Medical Research Involving Human Subjects Act (in Dutch: Wet Medisch-wetenschappelijk Onderzoek met Mensen)

## Summary

**Rationale:** colorectal polyps may harbor adenocarcinoma. Numbers are increasing due to the nationwide colorectal screening program. After endoscopic removal, rescue surgery is often performed because radicality can not be guaranteed by the pathologist. However, in 85% of surgical specimen no residual malignancy is found. Given morbidity and mortality associated with surgery a method to diagnose residual cancer is needed.

Biopsies from the polypectomy site are variably used to reduce the likelihood of residual tumor at the polypectomy site under these circumstances. However, the sensitivity of such biopsies is unknown.

Many patients are operated upon because of risk factors for dissemination such as lymphovascular invasion, despite a radical local resection. There has never been a prospective registration of these patients with regard to surgical outcome.

**Objectives:** 1 to evaluate the sensitivity of second-look endoscopic biopsies from the polypectomy site for residual tumor. 2. To register patients who do not fulfill inclusion criteria in order to evaluate their surgical outcomes.

**Study design:** prospective cross-sectional design using a multi-center approach.

**Study population:** patients in whom a malignant colonic polyp has been removed. For the biopsy part of the study (1) they should be planned for rescue surgery (including transmural excision) for the sole reason of (potentially) irradical endoscopic resection of a colorectal adenocarcinoma without poor differentiation, lymphovascular invasion or tumor budding and without other signs of dissemination.

**Intervention (biopsy part of the study):** endoscopic biopsies from the polypectomy site before operation. Patients who are excluded will only be registered.

**Main study parameters/endpoints:** Biopsy part of the study: sensitivity of second-look biopsies from the polypectomy site for residual tumor in the resected bowel and postoperative mortality. Various other factors will be assessed that might be associated with residual cancer. Observational part of the study: The prevalence of patients with exclusion criteria and outcome of surgery in this group (observational part of the study).

**Nature and extent of the burden and risks associated with participation and benefit (only applicable for biopsy-part of the study):** Depending on the situation: a): In case a tattoo needs to be done of the polypectomy site before surgery, or an endoscopic full-thickness resection is done, taking biopsies will be of no extra burden; b): In case no endoscopy is indicated before surgery (including TEM / TAMIS), a sigmoidoscopy (lesion distal to the splenic flexure) or occasionally colonoscopy (proximal to the splenic flexure) needs to be arranged for the purpose of this study. A sigmoidoscopy takes 10-20 minutes. Preparation consists of two enemas or flavored polyethylene glycol solution, depending on

NL51461.078.15 / NCT02328664 Scar biopsies after malignant colorectal polypectomy of uncertain radicality

the local protocol. A colonoscopy takes 20-30 minutes. Preparation consists of drinking flavored polyethylene glycol solution, both usually done at home. Notice that the patient has recent experience with colonoscopy. If necessary, both investigations can be arranged under conscious sedation (the rule in colonoscopy), which also implies day-care admission.

The risk of complications of a second endoscopy is estimated < 1:5000. The benefit of a 2nd colonoscopy is the discovery of new polyps in 10-25% of cases.

## 1 Introduction and rationale

Colorectal carcinoma (CRC) is the second most important cause of cancer mortality in the Netherlands with 15.003 new cases (2014) and 4940 deaths in 2013. Colorectal cancer usually develops from an adenomatous polyp, which is primarily resected via colonoscopy. The number of colonoscopies has dramatically increased with the introduction of population-based screening for colorectal cancer (2014). One or more polyps are roughly found in 1 out of 3 colonoscopies, and may harbor adenocarcinoma in 3-9%. This is sometimes unsuspected: Kudo *et al* reported that 2.8% of benign looking colonic polyps harbor invasive cancer.

Unfortunately, the pathologist is sometimes unable to guarantee a radical endoscopic resection from an oncological point of view. The bowel wall is thin and margins for endoscopic resection are limited to the submucosal space, often less than 1 mm. En-bloc resection is often impossible or too dangerous (perforation). Thus, the majority of endoscopic resection specimens show a tumor-free resection margin < 1 mm or a resection margin that is impossible to evaluate due to piecemeal resection (multiple fragments). For these patients, additional surgery is advised. However, residual tumor at the polypectomy site in surgical rescue specimens is found in only 5 (uncertain radical) to 30% (certainly not radical) of patients.

Affected locoregional lymph nodes are also of concern, even when imaging studies are normal. They are, however, rarely encountered in case of a moderately to well-differentiated adenocarcinoma without risk factors for lymph node metastasis (deep (> 1mm) submucosal invasion, tumor budding, a poorly differentiated histology and/or invasion of lymphatic or blood vessels). If one or more of these risk factors for lymph node metastases are present, metastases can be found in 11-15% of these surgical specimens. In such cases, the decision to additional surgery is made independently of local radicality.

According to the Dutch Surgical Colorectal Audit (DSCA), 30-day mortality of surgery for colonic cancer in 2013 was 1.9% and it also has been demonstrated that 90-day mortality is 1,51 times the 30-day mortality. Thus, 90-days postoperative mortality of surgery for colonic cancer is estimated to be 2.8% overall and 12% for patients aged 70 and above. With the advance of endosurgical (TEM, TAMIS) or endoscopic full-thickness bowel wall resection (eFTR) techniques the risks of additional surgery (especially mortality) are reportedly reduced. Given these risks, a test to diagnose the presence of residual cancer before deciding to surgery would be ideal. In practice, biopsies are often taken from the polypectomy site to see whether tumor has remained. However, no data exist on the sensitivity of endoscopic biopsies from the polypectomy site for residual cancer.

NL51461.078.15 / NCT02328664 Scar biopsies after malignant colorectal polypectomy of uncertain radicality

Many patients in whom a malignant polyp has been removed endoscopically are operated for because of the presence of risk factors for lymphovascular invasion, even if the endoscopic resection has been radical.

In such patients, biopsies are not helpful.

These patients will be registered in the study database, as there is no prospective evaluation in the Netherlands of surgical outcomes of these patients.

## 2 Objectives

### 2.1 Primary Objective:

To study the diagnostic properties, expressed by the sensitivity, of biopsies from the site of a malignant polypectomy for residual adenocarcinoma, as compared to surgical rescue specimen in patients with (potentially) irradical endoscopic resection of a malignant colonic polyp.

### 2.2 Secondary Objectives:

[figure not shown]
- 90-day mortality after rescue surgery: the number of patients that died within 91 day after the operation for presumed residual adenocarcinoma
- The sensitivity of biopsies for residual cancer in the bowel wall: the number of patients with endoscopic biopsies containing adenocarcinoma divided by the number of patients with adenocarcinoma in the resected bowel wall (regardless of regional lymph nodes)
- The number of complications (defined according to GCP and the Dutch Association of Gastroenterology) after biopsies from the polypectomy: the number of patients with bleeding or perforation after taking biopsies from the polypectomy scar, requiring at least prolongation of treatment, or admission to hospital, or delay or speeding up rescue surgery. This up until the moment of surgery.
- The sensitivity of global endoscopic assessment of initial polypectomy as well as scar biopsies for residual cancer: the number of patients in whom the endoscopic resection was assessed as incomplete and who also have residual cancer in the surgically resected specimen divided by the total number of patients in whom the endoscopic resection was judged to be incomplete.
- The proportion of patients with residual cancer in the resected specimen if malignancy was unsuspected during the endoscopic polypectomy: the number of patients in whom the malignancy was initially unsuspected during endoscopic polypectomy and who also have residual cancer in the surgical specimen divided by the total number of patients in whom the malignancy was initially unsuspected during endoscopic polypectomy.
- The proportion of patients in whom exclusion criteria apply and the results of surgery / complications of surgery in these patients.

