#### 4.4 Sample size calculation

The overarching goal is to investigate whether second-look endoscopic biopsies after resection of a malignant polyp with uncertain pathological completeness can be used as a screening instrument to aid in the clinical decision whether rescue surgery should be performed or not. The specificity of second-look biopsies from the polypectomy site for residual malignancy is estimated to be near 100%, as it is reasonable to state that no person without residual malignancy in the bowel wall is likely to have tumor in second look biopsies, in other words, the false-positive rate will be approximately zero.

Accordingly, sample size calculations will be done on the basis of sensitivity, i.e. the number of patients with positive second-look biopsies divided by the number of patients who do have residual tumor in the resected specimen. We state that sensitivity should be at least 95% to be clinically relevant. A non-inferiority approach can be used to calculate sample size. In that case, the null-hypothesis states that sensitivity is significantly inferior to 95%. Because proof of exact equality to 95% is impossible, a pre-stated margin of non-inferiority of -5% (90% in our study) is accepted.

The distributions of the probabilities belonging to the null- (around  $p = 0.90$ ) and alternative (around  $p = 0.95$ ) hypothesis is binomial but may be approximated by a normal distribution for sample size calculation.

Using the normal approximation, it can be calculated that 184 patients need to be included to achieve a power of 0.80 with and a probability of falsely accepting biopsies as non-inferior ( $\alpha$ ) of 0.05.

Using binomial distributions, it can be shown that 194 patients need to be included to achieve this goal. We will use the latter number for a robust estimate of sample size.

We estimate incomplete data and / or refusal to participate in 1 out of 10 patients invited.

This calculates to a number of 216 patients with residual tumor to be invited. Depending on the prevalence of residual tumor, which is estimated to vary between 10 and 30% (average 20%) of all patients, a total of 1080 patients fulfilling the inclusion criteria need to be invited to accomplish this number.

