## **10 Statistical analysis**

All statistical analyses will be done in the Deventer Hospital, with support of the local department of clinical epidemiology ([name]). Final approval will be obtained from the department of biostatistics and epidemiology at the Erasmus Medical Center ([name]). In principle, sensitivity will be calculated by dividing the number of patients with positive biopsies by the number of patients with tumor in the bowel wall and / or resected lymph nodes. Separate analysis will be done for bowel wall affection (as opposed to lymphatic spread) only.

The above-mentioned factors of potential influence will be studied on associations with the presence or absence of tumor in the bowel wall and / or resected lymph nodes. This will be done by using an independent samples *t*-test in the case of continuous normally distributed variables; by nonparametric test (e.g. Mann-Whitney U-test) in case of non-normally distributed ordinal variables; by Chi-Square statistics in case of categorical variables and by multiple logistic regression to investigate multiple associations.

Missing data will be dismissed from the analysis: the main issue is, whether there are preoperative biopsies and a resection specimen. If one of both fails, the loss will be compensated by the inclusion of another patient, as long as the number of evaluable patients is not reached.

NL51461.078.15 / NCT02328664 Scar biopsies after malignant colorectal polypectomy of uncertain radicality

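### Section 2.2 labels as a sensitivity of the endoscopic assessment a ratio that is its positive predictive value

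*Protocol*

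**What the plan says.** The fourth secondary objective in Protocol Section 2.2 is headed "The sensitivity of global endoscopic assessment of initial polypectomy as well as scar biopsies for residual cancer". Its numerator is "the number of patients in whom the endoscopic resection was assessed as incomplete and who also have residual cancer in the surgically resected specimen". Its denominator follows: "divided by the total number of patients in whom the endoscopic resection was judged to be incomplete".

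The protocol defines sensitivity in three other places, each time for the biopsies:

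- Section 2.2, the bowel-wall bullet: patients with positive biopsies "divided by the number of patients with adenocarcinoma in the resected bowel wall".
- Section 4.4: "the number of patients with positive second-look biopsies divided by the number of patients who do have residual tumor in the resected specimen".
- Section 10: "sensitivity will be calculated by dividing the number of patients with positive biopsies by the number of patients with tumor in the bowel wall", extended there to tumor in resected lymph nodes.

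No other section redefines the endoscopic-assessment parameter. Section 10.2 sends the reader to Section 8.1.2, which covers postoperative mortality only.

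**The concern.** A resection judged incomplete is the positive result of the endoscopic assessment. Dividing by everyone with that result answers this question: of the patients flagged, how many have residual cancer? Sensitivity answers a different one: of the patients with residual cancer, how many were flagged?

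The difference matters for the purpose given in Section 4.4, which is to help decide whether rescue surgery is needed. The error of most interest there is a resection judged complete when cancer remains. Those patients are in neither the numerator nor the denominator of the stated ratio, so the miss rate cannot be read from it. A reader who sees the word sensitivity would assume that it can.

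**Working it through.** The protocol gives no numerical value for this parameter, so there is no figure to reproduce. The check is the algebra of the two-by-two table, followed by an illustration.

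**Cells.** The test is the endoscopic judgement (incomplete = positive). The reference is residual cancer in the resected specimen.

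- TP: judged incomplete, cancer present
- FP: judged incomplete, no cancer
- FN: judged complete, cancer present

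**Formulas.** With prevalence p, sensitivity Se and specificity Sp:

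- Ratio in the Section 2.2 bullet = TP/(TP + FP) = p·Se / [p·Se + (1 − p)(1 − Sp)], the positive predictive value.
- Sensitivity = TP/(TP + FN) = Se, in which p does not appear.

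When TP is above zero, the two are equal only if FP = FN.

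**Inputs.** Section 4.4 gives the prevalence of residual tumor, "which is estimated to vary between 10 and 30% (average 20%) of all patients". The protocol gives neither Se nor Sp for the endoscopic assessment. I assume 0.70 for both and then vary them.

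| Prevalence | TP share | FP share | Stated ratio | Sensitivity |
|---|---|---|---|---|
| 10% | 0.10 × 0.70 = 0.07 | 0.90 × 0.30 = 0.27 | 0.07/0.34 = 0.21 | 0.70 |
| 20% | 0.20 × 0.70 = 0.14 | 0.80 × 0.30 = 0.24 | 0.14/0.38 = 0.37 | 0.70 |
| 30% | 0.30 × 0.70 = 0.21 | 0.70 × 0.30 = 0.21 | 0.21/0.42 = 0.50 | 0.70 |

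In counts, take 100 patients at 20% prevalence: 20 have residual cancer, 14 of them are flagged and 6 are missed, and 24 of the 80 without cancer are flagged. The stated ratio is 14/38. Sensitivity is 14/20. The 6 missed cancers appear only in the second.

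**Range.** At 20% prevalence, with Se and Sp each varied from 0.5 to 0.9, the stated ratio runs from 0.20 (both 0.5) to 0.69 (both 0.9). The lower end is an uninformative assessment that flags half of all patients: it scores 0.20 by the protocol's formula, while its sensitivity is 0.50.

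**Reach.** The sample size in Section 4.4 rests on a biopsy sensitivity of 90% against 95%. The endoscopic ratio enters neither that calculation nor the stopping limits in Section 8.7.

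**The case against.** The strongest reply is that the formula may be intended and only the word wrong. The next bullet in Section 2.2 has the same structure: residual cancer among patients with a given endoscopic impression, divided by all patients with that impression. It is correctly called a proportion. This stands as far as it goes. The text does not show whether the label or the denominator is the slip, and renaming alone would remove the contradiction. Renaming would still leave the sensitivity named in the objective unreported.

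A second reply is that little is lost. Section 8.1.3.2 records the endoscopist's estimate of radicality and Section 8.1.3.7 records whether tumor is present, so the full table can be built at any time. The association analyses in Section 10 appear to cover endoscopic radicality as well, and they would include patients judged complete. This is fair and bears on severity. It does not correct the definition.

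A reader might also infer that the trial sets this figure against the biopsy sensitivity and that a planned comparison is therefore invalid. The protocol does not support that. Section 3 limits the aim to evaluating the biopsies, Section 10 specifies no comparison of visual assessment with biopsies, and the mention of scar biopsies in the bullet's title comes with no test. The risk is that readers compare two figures sharing one name, not that a hypothesis test goes wrong.

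**Conclusion.** The point holds as an error of definition in one descriptive secondary objective. The quantity defined is the positive predictive value, it is called a sensitivity, and the name contradicts the protocol's other three definitions.

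Under the assumed Se = Sp = 0.70, the reported figure would be 0.21 to 0.50 across the protocol's own prevalence range, against a sensitivity of 0.70. These values show how far the two quantities can diverge. They do not predict the trial's result, because the accuracy of the endoscopic assessment is not given. That the stated ratio depends on prevalence and omits missed cancers does not rest on the assumed values.

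The primary endpoint, the sample size and the stopping rule are untouched. It should be fixed before analysis, but it does not threaten the main conclusion.

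**What to change.** In Section 2.2, define the sensitivity of the endoscopic assessment as patients assessed as incomplete who have residual cancer, divided by all patients with residual cancer in the resected specimen. Keep the present ratio as a second measure, labelled positive predictive value. Reporting both settles the matter whichever half of the sentence was the slip.

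Apply this to the estimate of radicality recorded at the initial polypectomy (Section 8.1.3.2). Section 4.2 requires a planned resection of every participant in the biopsy part, so patients judged complete should also have a specimen and the missed cancers can be counted.

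If a second-look version is wanted, as the bullet's title may suggest, a new denominator is not enough. Section 8.1.3.4 lists findings at the second endoscopy but no judgement of completeness. The protocol must first state which findings, for example suspected residual cancer or a polypous remnant, count as a positive assessment.

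The cost is one rewritten sentence in Section 2.2, plus one more for the second-look rule if it is used. No new data are needed for the initial assessment.

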## 3 Study design

The study has a multicenter approach and a cross-sectional observational design. There is no comparison to a placebo-group or control group; the study merely intends to evaluate the

sensitivities of biopsies from the malignant colorectal polypectomy site for residual adenocarcinoma. A flow chart of the study procedures is given in figure 1:

3.1 Figure 1: flow chart

\* Endoluminal resection includes: Transanal Endoscopic Microsurgical excision (TEM), Transanal Minimal Invasive Surgery (TAMIS) or Endoscopic Full-thickness Resection (eFTR).

## 4 Study population

### 4.1 Population

The number of reported T1 colorectal carcinomas from the Dutch Cancer Registration in 2011 was 1065.

Data from the Integral Cancer Registration in the South of the Netherlands (covering 2.3 million inhabitants) are not included. Extrapolated to the whole population of the Netherlands (16.8 million inhabitants), the nationwide incidence of T1 colorectal carcinoma is estimated to be 1200-1250 cases. These numbers are expected to increase due to the implementation of a nationwide screening program for colorectal cancer.

An endoscopically removed polyp with uncertain radicality is not equivalent to a T1 carcinoma, as it is actually unknown if the tumor extends into the muscularis propria layer. However, if the latter is the case, endoscopic removal is usually impossible because of fixation and lack of elevation with submucosal injection (non-lifting sign).

According to the data of Cooper and Ikamatsu *et al*, 30-33% is treated by endoscopic removal without rescue surgery. On the other hand, we assume that in 20% of these tumors no attempt for endoscopic resection is undertaken (direct referral for surgery). Accordingly, 50% of all patients (nationwide 600 patients per year) with a T1 colorectal carcinoma are eligible for the study. Assuming patients who are unwilling or unable to participate, we estimate a nationwide number of 500 evaluable patients per year.

### 4.2 Inclusion criteria (biopsy part of the study)

In order to be eligible to participate in this study, a subject must meet all of the following criteria:

- Aged 18 or above.
- Endoscopically removed colorectal lesion with the following pathological characteristics:
  - A moderately-to-well differentiated adenocarcinoma.
  - If possible to judge: distance between adenocarcinoma and vertical or lateral resection margin is less than 1 mm.
  - In case of piecemeal resection: radicality cannot be assessed (mostly due to loss of orientation and multiple fragments).
  - Absence of / not assessable lymphatic / vascular invasion.
  - No tumor budding (only if specifically mentioned in the pathology report).
  - No deep submucosal invasion (> 1 mm)

- No suspicion of dissemination on the following investigations: serum carcino-embryonic antigen, a computer tomographic (CT) scan of the abdomen and a chest X-ray; in case of a rectal tumor (less than 15 cm from the anal verge): an additional magnetic resonance imaging of the rectum.
- Operation or endoscopic full-thickness resection (including Transanal Endoscopic Microsurgical excision (TEM), Transanal Minimal Invasive Surgery (TAMIS) or Endoscopic Full-thickness Resection (eFTR)) is advised in agreement with the Dutch Guideline on Colorectal cancer, planned and agreed on by the patient.
- Written informed consent is obtained.

